### **9.3. Supportive Care Guidelines**

Necessary supportive measures for optimal medical care will be given throughout the study. Sites should assess and provide prophylaxis for venous thromboembolism per standard of care.

Supportive care medications may be administered at the investigator's discretion and recorded in the CRF. However, medications are subjected to the exclusions listed in [Section 8.2](#).

Supportive care parameters such as ventilator settings will be collected in accordance with the Schedule of Events (Appendix 1).

Supportive care for study subjects will be according to investigative sites' institutional protocols, but in all cases clinical respiratory practices for this critically ill study population with COVID-19-associated ARDS are anticipated to conform to the recommendations and best practice guidelines of the Society of Critical Care Medicine [Surviving Sepsis Campaign; Guidelines on the Management of Critically Ill Patients with Coronavirus 2019 (COVID-19), published 3/20/2020].

## **10. ASSESSMENTS**

The study procedures to be conducted for each patient enrolled in the study are presented in [Appendix 1](#).

Any deviation from protocol procedures should be documented and explained in the source documents. The sponsor (or designee) and the site's IRB (as required by the IRB's policies and procedures) should be notified as soon as possible of any substantial deviations potentially affecting patient safety, study drug administration or the assessment of safety, efficacy, and tolerability parameters.

### **10.1. Safety Assessments**

Safety assessments will consist of monitoring and recording all AEs. Safety will be assessed on the basis of treatment-emergent AEs, physical examination findings, clinical laboratory tests, electrocardiogram (ECG) measurements, and vital sign measurements.

#### **10.1.1. Clinical Assessments**

See the following clinical assessments are defined when referenced in the schedule of events ([Appendix 1](#)) for a list of clinical assessments.

#### **10.1.2. Laboratory Assessments**

Clinical laboratory tests during the study will be performed by local laboratories to facilitate standard care of the study subjects.

A laboratory abnormality reported by the local laboratory may meet the criteria to qualify as an AE or SAE as described in this protocol. In these instances, the AE corresponding to the laboratory abnormality will be recorded on the Adverse Event electronic CRF.

For laboratory abnormalities meeting the criteria of SAEs, the site must fax or email the SAE report including the laboratory report (as regionally required) to the sponsor using the SAE form.

The investigator must assess all abnormal clinical laboratory results for clinical significance in a timely fashion. A notation of clinically significant (CS) or non-clinically significant (NCS) with initials and date will be documented on the respective laboratory report next to any abnormal value. Information on laboratory AE reporting can be found in [Section 10.2.3](#).

The following laboratory assessments are defined as referenced in the schedule of events ([Appendix 1](#)) for this study:

- Serum or urine pregnancy
- Hematology/Serum Chemistry performed by local lab: CBC with differential and platelet; sodium, potassium, chloride, CO2, BUN, creatinine, total protein/albumin, AST/ALT, and total bilirubin. Direct bilirubin, triglycerides, C-reactive protein, and troponin to be assessed at baseline only unless clinically indicated. If baseline troponin is above ULN, the highest post-baseline value during hospitalization and the value closest to the date of discharge will also be recorded.

- Pharmacokinetic sampling for central lab analysis
- Cytokines collected for central lab analysis: IL-1 beta, IL-6, TNF-alpha, IL-10
- Viral load: Testing by qPCR of sample collected by nasopharyngeal swab unless subject is intubated, in which case, pulmonary sample to be used
  - Initial testing by local lab for eligibility
  - Duplicate swab will be collected at enrollment for Central Laboratory analysis
  - All subsequent weekly viral load specimens will be run by the Central Laboratory

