in inflammatory cytokines including TNFa, IL-1b & IL-6), as well as SOD data in influenza pulmonary models. The second application is in an overlapping population displaying hemodynamic instability for the treatment of hypotension refractory to vasopressor therapy, based on LPS and live E. coli challenge models. Third, emerging reports of significant kidney injury and cardiac myopathy among critically ill COVID-19 patients suggest further potential roles for GC4419 in preventing inflammatory damage to these organs, based on the known action of O2- in driving myocardial ischemia/reperfusion injury and doxorubicin cardiotoxicity, as well as cisplatin kidney injury.

For the oral mucositis indication, at the intended dose and schedule of 90 mg by 60-minute IV infusion M-F for 7 weeks, GC4419 demonstrated efficacy in the proposed indication in a randomized, double-blind, three-arm Phase 2b trial in which patients receiving standard chemoradiotherapy for locally advanced head and neck cancer received either 90 mg or 30 mg of GC4419 or placebo. GC4419 did not increase the known adverse effects of the chemoradiotherapy in this trial; the adverse event profiles for each active arm and the placebo control arm were similar.

Adverse effects attributable to GC4419 in clinical development are limited, with the principal adverse effect being mild, transient postural symptoms or hypotension at the end of the one-hour infusion, and to mild circumoral paresthesia, both attributable to transient potentiation of nitric oxide (NO). Data in humans and animals have demonstrated that these effects, which are related to Cmax, are further limited by lowering the dose or prolonging the infusion time of GC4419.

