### **10.5.2. All Adverse Events (AEs) Regardless of Seriousness**

Any adverse medical condition or laboratory abnormality with an onset date before the date of the baseline visit is considered to be pre-existing in nature, and part of a subject's medical history. Adverse medical conditions that begin on or after date of baseline visit will be considered an AE, including SAEs, and followed for 30 days after end of treatment GC4419/placebo. Similarly, new events will be reported as AEs/SAEs if the start date is within 30 Day Follow-up Period. Increases in toxicity grade of pre-existing conditions that occur on or after the date of the baseline visit are also considered an AE.

All AEs must be recorded in the patient's source documents and on the CRF regardless of frequency, severity (grade) or assessed relationship to study drug.

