## **11.6. Safety Analysis**

Adverse events will be grouped by system organ class, high level term, and preferred term according to the Medical Dictionary for Regulatory Activities (MedDRA) dictionary. Incidence by subject will be tabulated for all treatment emergent, serious, severe, and treatment-related AEs. Detailed listings will be provided for all SAEs, deaths, and withdrawals due to AEs.

Laboratory measurements, vital signs, and ECG parameters will be summarized by treatment group at each of the protocol specified time points.

Further details will be provided in the trial's statistical analysis plan.

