 Record worst value once a day assessed 8am-6pm

 <https://intensivecarenetwork.com/Calculators/Files/Apache4.html>. Record worst value in past 24 hours at baseline visit only.

 Record highest value during any 24-hour period

 Performed locally. CBC with differential and platelets; sodium, potassium, chloride, CO2, BUN, creatinine, total protein/albumin, AST/ALT, and total bilirubin. Include direct bilirubin, triglycerides, C-reactive protein, and troponin at baseline only unless clinically indicated. If baseline troponin is above ULN, the highest post-baseline value during hospitalization and the value closest to date of discharged will also be collected. Record Worst Value for Any Day When Multiple Labs are Drawn.

 Administer 90 mg IV over 180 minutes, Q 12 hours (+/- 2 hours) for 7 days. It is acceptable for the timing of the first 2 doses to be modified in order to accommodate subsequent dosing on a Q12 hour schedule that meets institution's standard of care procedures. *Study drug infusions should not begin if the subject's mean arterial pressure (MAP) is less than 65 mmHg.*

 Collected once during screening/baseline, at Day 7 and Day 14 (while in the hospital); blood sample to be stored on site for analysis by central lab at end of study

 IL-1 beta, IL-6, TNF-alpha, IL-10

 Screening sample to be performed by local lab with a duplicate sample collected for central lab analysis. Subsequent samples collected at Day 7 and Day 14 (while in the hospital) for central lab analysis. Nasopharyngeal sample required unless subject is intubated, in which case pulmonary secretion collected.

 If viral load test has been performed within 7 days of baseline, no repeat is necessary at baseline

 Collected pre and post first infusion on Day 1 and Day 3 for central lab analysis

 Adverse Events will be assessed weekly after hospital discharge, for a total of 6 weeks from Day 1 and encompassing at least 30 days after end of GC4419/placebo dosing. Post-treatment AE assessments may be done on an outpatient basis for subjects who are discharged from the hospital.

 As Clinically Indicated, Record Worst Value for Any Day When Multiple Labs are Drawn.

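### In subjects with normal baseline troponin no later troponin is scheduled and no peak or discharge value is required, so new-onset elevation cannot be tabulated consistently by arm

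*Combined protocol and SAP*

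**What the plan says.** Section 10.1.2 lists troponin with three other tests that are not repeated routinely: "troponin to be assessed at baseline only unless clinically indicated". The next sentence sets a follow-up rule for one group: "If baseline troponin is above ULN, the highest post-baseline value during hospitalization and the value closest to the date of discharge" will also be recorded.

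Appendix 1, footnote 9, repeats both parts. The schedule is "Include direct bilirubin, triglycerides, C-reactive protein, and troponin at baseline only unless clinically indicated", and the follow-up rule is "If baseline troponin is above ULN, the highest post-baseline value during hospitalization and the value closest to date of discharged will also be collected". The footnote then closes with a general instruction for the laboratory panel that carries no baseline condition: "Record Worst Value for Any Day When Multiple Labs are Drawn".

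Section 10.5.2 requires all adverse events to be entered "on the CRF regardless of frequency, severity (grade) or assessed relationship to study drug". Section 11.6 plans that "Laboratory measurements, vital signs, and ECG parameters will be summarized by treatment group at each of the protocol specified time points".

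On cardiac effects, Section 4.3 says that reports of kidney injury and cardiac myopathy in critically ill patients "suggest further potential roles for GC4419 in preventing inflammatory damage to these organs". Section 7.3 also names cardiac damage among the harms that the drug may attenuate.

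**The concern.** The explicit rule follows subjects whose troponin is already raised and sets no matching requirement for those in whom a rise would be new. For a safety comparison the second group is the more informative one. A shift from normal to above ULN, compared by arm, bears on both new cardiac harm and the cardiac protection that the rationale suggests.

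The Synopsis describes the trial as an initial assessment to confirm safety in this population, and Section 5.2 makes safety a secondary objective. If post-baseline troponin is collected reliably only in a subgroup defined by its baseline value, the trial may end without a usable by-arm account of new elevation, even where the values sit in the hospital chart.

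**Working it through.** The plan states no figure to reproduce. The check sets the relevant rules side by side and asks how a new troponin rise would be recorded in a subject with a normal baseline.

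1. **Scheduled measurement.** None. Section 10.1.2 and footnote 9 agree that troponin is taken at baseline and otherwise only when clinically indicated. This is also true of subjects with a raised baseline: their rule says which values to record but schedules no draw.

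2. **Explicit peak and discharge rule.** It does not apply, because its condition is a baseline above ULN. It also names no equivalent of the discharge value for a subject who dies in hospital.

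3. **Worst-value instruction in footnote 9.** This could be read as covering any clinically indicated troponin, since troponin belongs to the panel that the footnote describes. However, it says which value to enter on a day with several draws. It does not say that every clinically indicated troponin must be entered. If it did, the separate instruction to collect the highest value in subjects with a raised baseline would add nothing as to the peak. The word *also* in that instruction points the other way, towards an addition to general recording. Sites could reasonably differ.

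4. **Adverse event route.** A recognised cardiac diagnosis is an adverse event whatever the baseline troponin (Sections 10.4.1 and 10.5.2). A rise seen only in the laboratory is different. Section 10.5.3 does not report abnormal findings associated with the disease unless the investigator judges them more severe than expected. It admits a laboratory abnormality to the adverse event page only if it is an SAE, is specifically treated, leads to discontinuation of study drug, or is a new Grade 3 or 4 finding more severe than expected. Section 4.1.1 lists cardiac damage among the comorbidities of critical COVID-19. A troponin rise can therefore be attributed to the disease and left out. In addition, Section 10.1.2 sends the reader to Section 10.2.3 for laboratory adverse event reporting, but 10.2.3 is the list of post-ICU assessments.

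5. **ECG.** Section 10.1 counts ECG among the safety measures, but Section 10.2.1 and the Appendix 1 table place it at screening/baseline only. It does not fill the gap.

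6. **Planned table.** Section 11.6 summarises laboratory data at protocol-specified time points. Troponin has no such time point after baseline, so the section does not by itself produce a post-baseline troponin summary. It leaves further detail to the statistical analysis plan, but an analysis plan can tabulate only what was collected.

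**Size.** With 25 subjects per arm and a fraction p above ULN at baseline, 25 × (1 − p) subjects per arm fall outside the explicit rule. The documents give neither p nor the rate of new elevation, so neither this count nor the number of unrecorded rises can be computed.

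**The case against.** The strongest reply is that recognised heart injury is already captured. Clinically indicated testing is allowed. Section 10.1.2 requires the investigator to assess every abnormal result and mark its clinical significance on the report. All adverse events go on the CRF, including conditions newly diagnosed after dosing, and footnote 9's worst-value instruction has no baseline condition. All of this stands. A reader might infer from the follow-up rule that post-baseline troponin is recorded only in subjects with a raised baseline, or that new injury in the others has no required record. The documents do not support either reading.

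A second reply is that troponin is not a primary, secondary or exploratory endpoint, and that the cardiac text is background. The anticipated toxicity, hypotension, is monitored directly: before each infusion, every 30 minutes during it, at its end, and 1, 2 and 4 hours afterwards. This also stands, and it limits the weight of the point. It does not answer the gap in the safety data, because blood pressure does not show whether myocardial injury occurred.

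A third reply is that recording values already drawn leaves testing to clinical judgement, so a shift table would contain a not-measured group that is not random. That is correct, and the table must be read with that caveat.

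A reader might also infer that the rule would bias the comparison between arms by a stated amount, through differing draw counts or missing discharge values. The documents give no draw counts, no troponin rates and no number of subjects with a raised baseline, so no such amount can be supported.

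**Conclusion.** The point holds as a gap in systematic capture. In subjects with normal baseline troponin, the protocol schedules no later measurement and requires no peak or discharge value. What remains is clinically indicated testing with ambiguous recording, and adverse event reporting that may exclude rises associated with the disease. New-onset elevation cannot be tabulated consistently by arm.

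The size is unknown and cannot be derived from the documents. The conclusion rests on the text of Sections 10.1.2, 10.5.3 and 11.6 and Appendix 1, and on no assumed rate. The primary analysis is unaffected. This is an inexpensive improvement to safety data in a trial of about 50 subjects meant as an initial safety assessment.

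**What to change.** In Section 10.1.2 and Appendix 1, footnote 9, delete the condition that baseline troponin be above ULN. For every subject, record the troponin values already drawn in hospital: at least the highest, and the last before discharge or death. Enter each with its date and as a multiple of the local ULN, since local laboratories are used.

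Add to Section 11.6 a descriptive by-arm shift table. The rows are baseline normal or above ULN; the columns are post-baseline normal, above ULN or not measured. State beneath it that testing was clinically driven, so the not-measured column must be considered before arms are compared.

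The cost is two wording edits, a small CRF change, one table and a little extra chart abstraction for about 50 subjects. No additional blood test is needed. The limitation is that ascertainment still depends on clinical practice, so a silent rise that nobody tests for will remain unseen.

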## **10.2. Schedule of Time and Events**

A schedule of study assessments table is located in [Appendix 1](#). Minor changes to the assessment schedule may be made to accommodate holidays, administrative closures, etc., which if necessary, are not considered as significant deviations by the Sponsor. Sites should contact the Sponsor (or its representative) prospectively to address rescheduling protocol assessments and data handling.

### **10.2.1. Screening Phase**

The following screening observations and procedures will be completed prior to Day 1:

- Obtain a signed IRB/IEC/REB-approved informed consent
- Confirm patient eligibility by reviewing inclusion/exclusion criteria
- Obtain medical history including comorbid conditions hypertension, diabetes, coronary artery disease, hyperlipidemia, asthma, other notable pre-existing conditions
- Record predicted body weight
- Record supplemental oxygen/ ventilation status and parameters
- Blood Pressure/MAP/vasopressor use
- Collect sample for laboratory assessments per Schedule of Assessments
- 12-lead ECG
- Review of concomitant medications
- Record SOFA and Apache IV score
- Record previous day's Daily Fluid Balance, if available

### **10.2.2. Hospitalization/Treatment Phase**

All subjects will receive standard supportive care according to the policies of the treating institution. Subjects will be randomized in a 1:1 ratio to receive either:

- GC4419 by IV infusion q 12 hours (+/- 2 hours), plus standard supportive care, or
- Placebo by IV infusion q 12 hours (+/- 2 hours), plus standard supportive care only

Subjects will receive, in a blinded fashion, either GC4419, 90 mg intravenously, or placebo, administered over 3 hours (180 minutes), repeated every 12 hours (+/- 2 hours) for 7 consecutive days. *Study drug infusions should not begin if the subject's mean arterial pressure (MAP) is less than 65 mmHg.*

The following observations and procedures will be completed per the schedule of assessments:

- Supplemental oxygen/ventilation status and parameters
- Blood Pressure/MAP
- SaO2 or PaO2/FiO2 ratio
- Collect sample for laboratory assessments per schedule of assessments
- Review of concomitant medications and adverse events
- SOFA scores
- Daily Fluid Balance
- Administer GC4419/placebo

#### **10.2.3. Post ICU Discharge**

The following observations and procedures will be completed per the schedule of assessments

- Blood Pressure/MAP
- SaO2 or PaO2/FiO2 ratio
- Collect sample for laboratory assessments per schedule of assessments
- Review of concomitant medications and adverse events

### **10.3. ADVERSE EVENTS AND SERIOUS ADVERSE EVENTS**

Adverse Events and Serious Adverse Events will be assessed daily during hospitalization and weekly after hospital discharge, for a total of 6 weeks after day 1 and encompassing at least 30 days after end of GC4419/placebo dosing (experimental arm subjects). Post-treatment AE assessments may be done on an outpatient basis for subjects who are discharged from the hospital.

The investigator is responsible for the detection and documentation of events meeting the criteria and definition of an AE or SAE as provided in this protocol. Throughout the study, AEs will be recorded in the source documents and on the appropriate pages of the CRF regardless of whether the AEs are considered related to GC4419/placebo. To avoid confusion, the AE should be recorded in standard medical terminology.

### **10.4. Definitions**

The following definitions of terms are guided by the International Conference on Harmonization and the U.S. Code of Federal Regulations (CFR) and are included here verbatim.

#### **10.4.1. Adverse Event (AE)**

An AE is any untoward medical occurrence in a patient or clinical investigation subject administered a pharmaceutical product and which does not necessarily have a causal relationship with this treatment. An AE can therefore be any unfavorable and unintended sign (including an abnormal laboratory finding), symptom, or disease temporally associated with the use of a medicinal (investigational) product, whether or not related to the medicinal (investigational) product.

**Examples of an AE include:**

- Significant or unexpected worsening or exacerbation of the condition/indication under study.
- Exacerbation of a chronic or intermittent pre-existing condition including either an increase in frequency and/or intensity (grade) of the condition.
- New conditions detected or diagnosed after investigational product administration even though they may have been present prior to the start of the study.
- Signs, symptoms, or the clinical sequelae associated with a suspected interaction of the investigational product with a concomitant medication.
- Signs, symptoms, or the clinical sequelae associated with a suspected overdose of either investigational product or a concurrent medication.

#### **10.4.2. Serious Adverse Event (SAE)**

Any untoward medical occurrence that at any dose:

- Results in death,
- Is life-threatening – *NOTE: The term 'life-threatening' in the definition of 'serious' refers to any adverse drug experience [adverse event] that places the patient or subject, in the view of the investigator, at immediate risk of death from the reaction as it occurred, ie, it does not include a reaction that, had it occurred in a more severe form, might have caused death.*
- Requires inpatient hospitalization or prolongation of hospitalization – *NOTE: In general, hospitalization signifies that the patient or subject has been detained (usually involving at least an overnight stay) at the hospital or emergency ward for observation and/or treatment that would not have been appropriate in the physician's office or outpatient setting. Complications that occur during hospitalization are AEs. If a complication prolongs hospitalization or fulfills any other serious criteria, the event is serious. When in doubt as to whether "hospitalization" occurred or was necessary, the AE should be considered serious. Hospitalization for elective treatment of a pre-existing condition that did not worsen from baseline is not considered an AE.*
- Results in persistent or significant disability/incapacity – *NOTE: The term disability means a substantial disruption of a person's ability to conduct normal life functions.*

OR

- Is a congenital abnormality/birth defect.
- Is an other important medical event

